3.3.3. Clinical Status At Specific Timepoints

The key secondary analyses include evaluation of the clinical status score at Day 15. For this outcome, Study Visit Day 15 is the timepoint of interest, not necessarily the actual study day. The score collected at the study visit corresponding to Day 15 will be used for this outcome. For analyses of this outcome, imputation of the clinical score may be performed following the rules described in Section 6.5.

Additional analyses are clinical status at Days 3, 5, 8, 11, 15, 22, and 29. As the with above, the scores that will be used are those collected at the study visits corresponding to those days.

Sensitivity analyses of the key secondary outcome will be performed where subjects who were unblinded and crossover treated with remdesivir prior to Day 15 will have their latest CSO score pre-remdesivir treatment carried forward to Day 15. A similar process will be used for the unblinding sensitivity analysis.

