8.1.2.2 Ordinal Scale

The ordinal scale is the primary measure of clinical outcome.

The scale used in this study is as follows (from worst to best):

- Death;
- Hospitalized, on invasive mechanical ventilation or ECMO;
- Hospitalized, on non-invasive ventilation or high flow oxygen devices;
- Hospitalized, requiring supplemental oxygen;

- Hospitalized, not requiring supplemental oxygen - requiring ongoing medical care (COVID-19 related or otherwise);
- Hospitalized, not requiring supplemental oxygen - no longer requires ongoing medical care;
 - This would include those kept in hospital for quarantine/infection control, awaiting bed in rehabilitation facility or homecare, etc.
- Not hospitalized, limitation on activities and/or requiring home oxygen;
- Not hospitalized, no limitations on activities

To determine a subject's clinical status using the ordinal scale: On Day 1, report their clinical status at randomization. On Day 2, report the period from randomization to midnight on Day 1. On Day 3 through Day 11, or until discharged, and on Days 15, 22 and 29, provide the worst clinical assessment for the previous day (i.e., midnight to midnight; 00:00 – 23:59 (24-hr clock)). For example, on study Day 3 when completing the form, the worse clinical outcome measure of Day 2 is captured with the worst being death followed by ECMO, mechanical ventilation, etc. The Day 2 measurement is assessed as occurring anytime in that 24-hour period (00:00 to 23:59).

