3. STUDY OBJECTIVES AND ENDPOINTS

3.1. Study Objectives

Primary Objective

The overall objective of the study is to evaluate the clinical efficacy of different investigational therapeutics relative to the control arm in patients hospitalized with COVID-19 as assessed by the time to recovery up to Day 29.

Secondary Objectives

The key secondary objective is to evaluate the clinical efficacy of different investigational therapeutics relative to the control arm in patients hospitalized with COVID-19 as assessed by the 8-point ordinal clinical status scale at Day 15.

The other secondary objectives are to:

1. Evaluate clinical efficacy of different investigational therapeutics as compared to the control arm as assessed by:
 - Clinical Severity
 - 8-Point Clinical Status Ordinal scale:
 - Time to an improvement of one category and two categories from Day 1 (baseline) on the clinical status 8-point ordinal scale.
 - Subject clinical status using 8-point ordinal scale at Days 3, 5, 8, 11, 15, 22, and 29.
 - Mean change in the clinical status 8-point ordinal scale from Day 1 to Days 3, 5, 8, 11, 15, and 29.
 - National Early Warning Score (NEWS):
 - Time to discharge or to a NEWS of ≤ 2 and maintained for 24 hours, whichever occurs first.
 - Change from Day 1 to Days 3, 5, 8, 11, 15, and 29 in NEWS.
 - Oxygenation:
 - Days requiring oxygen through Day 29.
 - Incidence and duration of new oxygen use through Day 29.
 - Non-invasive ventilation/high flow oxygen:
 - Days of non-invasive ventilation/high flow oxygen through Day 29.
 - Incidence and duration of new non-invasive ventilation or high flow oxygen use through Day 29.
 - Invasive Mechanical Ventilation / extracorporeal membrane oxygenation (ECMO):
 - Days of ventilator/ECMO through Day 29.

- Incidence and duration of new mechanical ventilation or ECMO use through Day 29.
 - Hospitalization
 - Duration of hospitalization (in days) through Day 29.
 - Mortality
 - 14-day mortality.
 - 28-day mortality.
2. Evaluate the safety of the intervention through 28 days of follow-up as compared to the control arm as assessed by:
- Cumulative incidence of SAEs through Day 29
 - Cumulative incidence of Grade 3 and 4 clinical and/or laboratory AEs through Day 29.
 - Discontinuation or temporary suspension of infusions (for any reason).

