Subjects will be assessed daily while hospitalized. If the subjects are discharged from the hospital, they will have a study visit at Days 15, 22, and 29. For discharged subjects, it is preferred that the Day 15 and 29 visits are in person to obtain safety laboratory tests and OP swab and blood (serum only) samples for secondary research as well as clinical outcome data. However, infection control or other restrictions may limit the ability of the subject to return to the clinic. In this case, these visits may be conducted by phone, and only clinical data will be obtained. The Day 22 visit does not have laboratory tests or collection of samples and may also be conducted by phone.

The primary outcome is time to recovery by Day 29. The primary analysis will include data from both severity groups using a stratified log-rank test. A key secondary outcome evaluates treatment-related improvements in the 8-point ordinal scale at Day 15. As little is known about the clinical course of COVID-19, an evaluation of the pooled (i.e., blinded to treatment assignment) proportion recovered will be used to gauge whether the targeted total number of subjects in the recovered categories of the ordinal scale will be achieved with the planned sample size. The analysis of the pilot data will be blinded, allowing for the pilot data to be included in subsequent analyses.

The study will randomize subjects 1:1 to placebo or investigational product. In absence of an established treatment, the use of placebo is justified. If additional arms are added to or dropped from the trial, randomization will proceed with an equal probability of assignment to each of the

remaining arms. Randomization will be stratified by site and severity (severe versus mild-moderate). See Section 4.2.3 for more information on randomization and stratification.

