6.5. Missing Data

All attempts will be made to collect all data per protocol. Any data point that appears to be erroneous or inexplicable based on clinical judgment will be investigated as a possible outlier. If data points are identified as outliers, sensitivity analyses may be performed to examine the impact of including or excluding the outliers. Any substantive differences in these analyses will be reported.

For time to event outcomes, subjects who are lost to follow-up or terminate the study prior to Day 29 and prior to observing/experiencing the event will be censored at the time of their last observed assessment. Subjects who die prior to observing/experiencing the event will be censored at Day 29.

For the analysis of the key secondary outcome, subjects who are discharged but are subsequently re-admitted prior to Day 15 without a reported clinical score, their clinical score will be imputed at 7, which is the highest value for a hospitalized subject.

For the analyses of the secondary outcomes that involve clinical score (i.e. the key secondary outcome and time to improvement), if a subject is discharged from the hospital without a previously or concurrently reported clinical score of 1 or 2, then their clinical score at the time of discharge will be imputed as 2, which is the highest value for a non-hospitalized subject.

For the modified version of the ordinal score described in Section 4.3, if a subject is discharged from the hospital without a previously or concurrently reported clinical score of 2 or 3, then their clinical score at the time of discharge will be imputed as 3, which is the highest value for a non-hospitalized subject.

For the analyses of the secondary outcomes described in Section 3.3, the following imputation rules will be used for subjects who are lost to follow-up, terminate early from the study, or do not have further outcome data available after discharge for any reason:

- Days of Non-invasive ventilation/high-flow oxygen:
 - If the subject's clinical status scale is 6 at the last observed assessment, then the subject will be considered to be on non-invasive ventilation/high-flow oxygen

- through Day 29. The endpoint will be total days when assessments are available plus all imputed days following the last observed assessment.

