Table 28: Time to Improvement on the 8-Point Ordinal Scale by Treatment Group – Remdesivir Retreatment Sensitivity Analysis on Subjects with Clinical Status Score of 7 at Enrollment

Table 29: Time to Improvement by at least Two Clinical Status Categories on the 8-Point Ordinal Scale by Treatment Group: Alternate Ordinal Scale

Table 30: Time to Improvement by at least One Clinical Status Category on the 8-Point Ordinal Scale by Treatment Group within Subgroups – ITT Population

Table 31: Time to Improvement by at least One Clinical Status Category on the 8-Point Ordinal Scale by Treatment Group within Subgroups – Treated Population

Table 32: Time to Improvement by at least Two Clinical Status Categories on the 8-Point Ordinal Scale by Treatment Group within Subgroups – ITT Population

Table 33: Time to Improvement by at least Two Clinical Status Categories on the 8-Point Ordinal Scale by Treatment Group within Subgroups – Treated Population

Programming notes for Tables 30 – 33:

Instead of the “Analysis Population” column, a column titled “Grouping Variable” will be to the left of Treatment Group. Rows will be generated for each subgroup.

Table 34: Clinical Status Scores by Treatment Group and Study Visit – ITT Population

Study Visit	Ordinal Scale Measure	Remdesivir (N=X)			Placebo (N=X)			All Subjects (N=X)		
		n	%	95% CI	n	%	95% CI	n	%	95% CI
Day 1	Death at or before Study Visit (8)	x	x	x.x, x.x	x	x	x.x, x.x	x	x	x.x, x.x
	Hospitalized, on invasive mechanical ventilation or ECMO (7)	x	x	x.x, x.x	x	x	x.x, x.x	x	x	x.x, x.x
	Hospitalized, on non-invasive ventilation or high flow oxygen devices (6)	x	x	x.x, x.x	x	x	x.x, x.x	x	x	x.x, x.x
	Hospitalized, requiring supplemental oxygen (5)	x	x	x.x, x.x	x	x	x.x, x.x	x	x	x.x, x.x
	Hospitalized, not requiring supplemental oxygen - requiring ongoing medical care (COVID-19 related or otherwise) (4)	x	x	x.x, x.x	x	x	x.x, x.x	x	x	x.x, x.x
	Hospitalized, not requiring supplemental oxygen - no longer requires ongoing medical care (3)	x	x	x.x, x.x	x	x	x.x, x.x	x	x	x.x, x.x
	Not hospitalized, limitation on activities and/or requiring home oxygen (2)	x	x	x.x, x.x	x	x	x.x, x.x	x	x	x.x, x.x
	Not hospitalized, no limitations on activities (1)	x	x	x.x, x.x	x	x	x.x, x.x	x	x	x.x, x.x
	No clinical status score reported – Hospitalized subjects	x	x	x.x, x.x	x	x	x.x, x.x	x	x	x.x, x.x
	No clinical status score reported – Discharged subjects	x	x	x.x, x.x	x	x	x.x, x.x	x	x	x.x, x.x

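### Mean change in the ordinal scale at Days 3 to 11 has no score for subjects already discharged alive, so the listed secondary outcome is biased toward no effect

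*SAP*

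**What the plan says.** SAP 3.1 lists, among the other secondary objectives, "Mean change in the clinical status 8-point ordinal scale from Day 1 to Days 3, 5, 8, 11, 15, and 29". The protocol lists the same outcome in Section 3, and its Section 9.4.3 (item 3) summarises change at specific time points by the proportions improving or worsening by 1 to 4 points.

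Protocol 8.1.2.2 sets when scores are recorded after Day 2: "On Day 3 through Day 11, or until discharged, and on Days 15, 22 and 29". SAP 4.1 agrees on follow-up: "If the subjects are discharged from the hospital, they will have a study visit at Days 15, 22, and 29". Scoring therefore stops at discharge and resumes at Day 15.

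SAP 3.3.3 allows imputation in its paragraph on the Day 15 outcome. Its next paragraph, on the full list of visit days, says only: "As the with above, the scores that will be used are those collected at the study visits corresponding to those days".

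SAP 6.5 has a discharge rule. Its scope is "For the analyses of the secondary outcomes that involve clinical score (i.e. the key secondary outcome and time to improvement", and for a subject discharged without a reported 1 or 2 it says "then their clinical score at the time of discharge will be imputed as 2". It does not say that the value is carried to later visit days. The readmission rule in the same section (score 7 if no score is reported) is confined to the key secondary outcome.

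The Table 34 shell has a row "Death at or before Study Visit (8") and a separate row "No clinical status score reported – Discharged subjects". It defines N as the ITT population. SAP 8.2.1 and the list of tables contain no method, shell or missing-score rule for mean change in the ordinal scale.

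**The concern.** A subject discharged alive on Day 5 is in category 1 or 2 by the definition of the scale, yet has no Day 8 or Day 11 score. A mean of collected scores is then a mean over subjects still in hospital and, if they are handled as in Table 34, those who have died. That subset is selected by outcome and shrinks faster in the arm that discharges sooner. The best known outcome is treated as missing while the worst is kept. If the arms do not differ this does no harm. If the drug works, the comparison is diluted.

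The protocol's improvement proportions have the same problem, because a subject without a score cannot be counted as improved.

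SAP 2.1 records that version 3.0 was written after the interim results had been presented and disclosed. A rule left open here would be chosen during programming with results already known.

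**Working it through.** **1. Reproduce the SAP's own figure.** The documents give no distribution for Days 3 to 11, so the nearest available input is the Day 15 control distribution (SAP Table 4) with an odds ratio of 1.75 (SAP Table 6). Scenario 1, scores 8 down to 1, is 2, 1, 2, 7, 8, 10, 30, 40%. Dividing each cumulative odds from the worst category by 1.75 gives, for treatment, 1.15, 0.58, 1.18, 4.31, 5.27, 7.17, 26.48, 53.85%, which matches Table 6 to rounding.

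The SAP's sample size formula, with p_i averaged over the two arms:

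N = 12(1.960 + 1.036)² / [(ln 1.75)² (1 − Σp_i³)] = 107.74 / [0.3132 × (1 − 0.127)] = 394

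The SAP states 396, so the inputs are read correctly.

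**2. Mean score three ways, Scenario 1.** With balanced baselines, the arm difference in mean score equals the difference in mean change. Categories 3 to 8 hold 30% of control and 19.67% of treatment, and their score-weighted sums are 1.32 and 0.8455.

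- True scores known: 2.32 v 1.914, difference 0.406.
- Discharged scored 2: 1.32 + 2 × 0.70 = 2.72, against 0.8455 + 2 × 0.8033 = 2.452; difference 0.268.
- Discharged omitted, deaths at 8: 1.32/0.30 = 4.400, against 0.8455/0.1967 = 4.298; difference 0.102.

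The share remaining is 0.102/0.406 = 25% of the true difference and 0.102/0.268 = 38% of the score-2 difference.

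**3. All five SAP scenarios, odds ratio 1.75.** The last column is the odds ratio from a proportional odds fit to categories 3 to 8 only.

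| Scenario | Control discharged | True diff. | Score-2 diff. | Omitted diff. | % of true | % of score-2 | Apparent OR |
|---|---|---|---|---|---|---|---|
| 1 | 70% | 0.406 | 0.268 | 0.102 | 25 | 38 | 1.15 |
| 2 | 81% | 0.297 | 0.158 | 0.060 | 20 | 38 | 1.09 |
| 3 | 75% | 0.345 | 0.206 | 0.075 | 22 | 36 | 1.12 |
| 4 | 53% | 0.436 | 0.311 | 0.131 | 30 | 42 | 1.25 |
| 5 | 33% | 0.496 | 0.410 | 0.220 | 44 | 54 | 1.40 |

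**4. Smaller discharged shares.** This range is an assumption. The Scenario 1 and 5 control distributions were shifted by a constant on the cumulative logit scale to reach each share, and the odds ratio of 1.75 was then applied. Where two values are given, they span the two scenarios.

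| Control discharged | % of true remaining | % of score-2 remaining | Apparent OR |
|---|---|---|---|
| 1% | 85-92 | 86-93 | 1.74 |
| 5% | 77-83 | 78-85 | 1.69 |
| 10% | 69-73 | 71-77 | 1.63 |
| 20% | 57-58 | 61-65 | 1.52 |
| 30% | 47-48 | 54-56 | 1.43 |
| 40% | 38-41 | 48-49 | 1.35 |
| 50% | 31-35 | 44 | 1.27 |
| 60% | 26-30 | 39-41 | 1.21 |

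More than half of the true difference is lost only once about 30% of controls have been discharged. In every case computed the difference keeps its sign and shrinks.

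**The case against.** The strongest reply is that the SAP has not chosen a biased mean-change analysis; it has specified none. The sentence in 3.3.3 is about clinical status, and that deaths enter the mean as 8 is inferred from a row label in Table 34. Both points are fair. But mean change is built from the same visit-day scores, 3.3.3 is the only text saying which scores those are, and 6.5 names the outcomes that its discharge rule covers. A programmer following the text has no score to use for a discharged subject.

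A reader might infer that discharged subjects also vanish from the by-visit status table. They do not: Table 34 gives them their own row, and N is the ITT population. On that base, faster discharge shows as a larger discharged row. Only the non-missing denominator that SAP 6.1 offers as an example would distort the percentages. The images for Figures 13 and 14 are not available, so nothing can be said about them.

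A reader might also infer that the effect is largely lost on every day, or that the result could point the wrong way. The documents support neither. Anticipated discharge within 72 hours is an exclusion and the Day 3 form records Day 2, so few discharges should affect Day 3. An illustrative multistate model can produce a 0.04-point reversal in the raw Day 11 mean (5.83 control v 5.87 treated), but it rests on an assumed baseline mix and assumed transitions, and mean change does not reverse even there.

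Finally, the consequences are limited. By-visit status is descriptive with no planned test, and discharge is properly counted in time to recovery, the Day 15 outcome and time to improvement. That argues for a modest priority, not for leaving the gap.

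**Conclusion.** The point holds for mean change in the ordinal scale at Days 3, 5, 8 and 11, and for the protocol's improvement proportions on those days. As written, subjects discharged alive have no score, and an effective drug would look less effective than it is. With the SAP's Day 15 scenarios as a proxy, 20-44% of the true mean difference remains, or 36-54% of what a score-2 rule would show. At 10% of controls discharged, 69-73% of the true difference remains.

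This rests on proportional odds with an odds ratio of 1.75, balanced baselines, deaths entering as 8, and Day 15 shapes standing in for earlier days. The actual discharged share on Days 3 to 11 is not in the documents; the loss is probably minor at Day 3 and grows as discharges accumulate. The change should be made, but no primary or key secondary conclusion depends on it.

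**What to change.** In SAP 3.3.3 and 6.5, state that for mean change and for the 1- to 4-point improvement proportions at Days 3 to 11:

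- a subject discharged alive carries the last reported score of 1 or 2, or otherwise 2, from discharge until the next reported score or readmission;
- on readmission without a reported score, the existing readmission rule in 6.5 is extended to these summaries;
- deaths carry 8.

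Add an analysis paragraph and a table shell for mean change, report the number imputed by arm and day, and add a sensitivity analysis using score 1. Keep the separate discharged row in Tables 34 and 35, and fix the percentage base as the whole population: ITT in Table 34 and, correspondingly, treated in Table 35.

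The cost is a few sentences, one shell and an extension of a rule that 6.5 already contains; no new data are needed. The drawback is that categories 1 and 2 cannot be separated before Day 15, so part of the true difference is still missed: in Scenario 1 the score-2 rule shows 0.268 of 0.406, or 66%. An apparent shift from 2 to 1 at Day 15 may also arise from the rule alone, which is why the imputed counts should be shown.

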3.3.4. Time to Clinical Status Improvement

Additional analyses will evaluate the time to improvement of at least one point on the clinical status 8-point ordinal scale. That is, improvement will be defined as a decrease of at least one point on the 8-point scale compared to the baseline value (e.g. from 5 to 4; from 5 to 3) and the time to improvement will be defined as the elapsed time (in days) from randomization to the

earliest day of observed improvement. Note that since clinical status assessments are recorded as defined in Section 4.3, the day that is being assessed (not necessarily the day the response is collected) will be used to determine the timing of events.

For analyses of this outcome, imputation of the clinical score may be performed following the rules described in Section 6.5.

Any subjects that are lost to follow-up or terminated early prior to an observed improvement will be censored at the day of their last observed assessment. Subjects who complete follow-up but do not experience improvement will be censored at the day of their Day 29 visit. All deaths within Day 29 (and prior to improvement) will be considered censored at 28 days.

An alternative definition of improvement will also be used where improvement will be defined as a decrease of at least two points on the 8-point scale compared to the baseline value (e.g. from 5 to 3; from 5 to 2). The timing and censoring definitions will follow similarly to the above.

Sensitivity analyses will be performed where subjects who were unblinded and retreated with remdesivir will be censored at the time of remdesivir treatment initiation. A similar process will be used for the unblinding sensitivity analysis.

3.3.5. Time to Discharge or NEWS of ≤ 2

The time to discharge or NEWS of ≤ 2 will be defined as the elapsed time (in days) from baseline to the earliest day at which either of the following occur:

- Discharge from hospital
- Reported NEWS of ≤ 2 which is maintained for 24 hours

For the latter bullet, to meet this criterion, scores of ≤ 2 must be reported on consecutive study visits. The timing of the event will be set to the day of the second assessment.

All deaths that occur before discharge or before an observed NEWS of ≤ 2 will be considered censored at 28 days.

3.3.6. Days of Non-invasive ventilation/high-flow oxygen

Non-invasive ventilation/high flow-oxygen days will be defined as the number of days where the clinical status score is equal to 6. After discharge, the CRF question regarding days of ventilation will be used. The total number of days will be the sum of all reported days, regardless of whether the days occur consecutively or in disjoint intervals. See Section 6.5 for the plan for handling subjects who do not have data through Day 29 or die prior to Day 29.

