3.3.7. Days of Ventilation/ECMO

Ventilator / ECMO days will be defined as the number of days where the clinical status score is equal to 7. After discharge, the CRF question regarding days of ventilation will be used. The total number of days will be the sum of all reported days, regardless of whether the days occur consecutively or in disjoint intervals. See Section 6.5 for the plan for handling subjects who do not have data through Day 29 or die prior to Day 29.

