3.3.8. Days of Oxygen

Oxygen days will be defined as the number of days where the clinical status score is equal to 5, 6, or 7. After discharge, the CRF question regarding days of oxygenation will be used. The total number of days will be the sum of all reported days, regardless of whether the days occur consecutively or in disjoint intervals. See Section 6.5 for the plan for handling subjects who do not have data through Day 29 or die prior to Day 29.

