- If the subject is not on non-invasive ventilation/high-flow oxygen at the last observed assessment, then the subject will be considered to not be on non-invasive ventilation/high-flow oxygen for the remainder of follow-up. Thus, no additional imputed days will be added to the number of days recorded on available assessments.
 - Days of ventilation/ECMO:
 - If the subject's clinical status scale is 7 at the last observed assessment, then the subject will be considered to be on ventilation/ECMO through Day 29. The endpoint will be total days when assessments are available plus all imputed days following the last observed assessment.
 - If the subject is not on ventilation/ECMO at the last observed assessment, then the subject will be considered to not be on ventilation/ECMO through Day 29. Thus, no additional imputed days will be added to the number of days recorded on available assessments.
 - Days of Oxygen:
 - If the subject's clinical status score is 5, 6, or 7 at the last observed assessment, then the subject will be considered to be on oxygen through Day 29. The endpoint will be total days when assessments are available plus all imputed days following the last observed assessment.
 - If the subject is not on oxygen at the last observed assessment, then the subject will be considered to not be on oxygen through Day 29. Thus, no additional imputed days will be added to the number of days recorded on available assessments.
 - Days of Hospitalization
 - If the subject is discharged and no further hospitalization data are available, then the subject will be assumed to not have been readmitted. Thus, no additional imputed days will be added to the number of days recorded on available assessments. If a subject dies while hospitalized, the number of days of hospitalization will be imputed as 28 days.

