8.2.5. Days of Non-Invasive Ventilation/High-Flow Oxygen

Duration of non-invasive ventilation/high flow oxygen days will be summarized in a table using medians and quartiles by treatment arm. This will only include subjects in category 6 or 7 at enrollment. Analyses will be performed in the ITT population, Treated population, and a subset of the Treated population of treated subjects only as subjects who are not treated are terminated from the study immediately and are included in the ITT/Treated analyses with a count of 1 day. Bee swarm plots of non-invasive ventilation/high flow oxygen days by treatment arm will be generated, where subject whose days are imputed to the maximum of 28 days due to death are grouped separately from subjects who do not die.

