8.2.7. Days of Invasive Mechanical Ventilation/ECMO

Duration of invasive Mechanical Ventilation/ECMO days will be summarized in a table using medians and quartiles by treatment arm. This will only include subjects in category 7 at enrollment. Analyses will be performed in the ITT population, Treated population, and a subset of the Treated population of treated subjects only as subjects who are not treated are terminated from the study immediately and are included in the ITT/Treated analyses with a count of 1 day. Bee swarm plots of invasive Mechanical Ventilation/ECMO days, and days hospitalized by treatment arm will be generated, where subject whose days are imputed to the maximum of 28 days due to death are grouped separately from subjects who do not die.

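### Non-invasive ventilation/high-flow days count score 6 only but are summarized in subjects starting at 6 or 7, so among survivors more time on the ventilator can mean fewer days (minor)

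*SAP*

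**What the plan says.** Four SAP rules fix this outcome.

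- **Count (3.3.6).** In-hospital days "will be defined as the number of days where the clinical status score is equal to 6". After discharge, days come from the CRF question on ventilation.
- **Population and statistic (8.2.5).** Medians and quartiles by arm. "This will only include subjects in category 6 or 7 at enrollment".
- **Incomplete follow-up (6.5).** Days are carried to Day 29 only if the "clinical status scale is 6 at the last observed assessment". Otherwise the subject is "considered to not be on non-invasive ventilation/high-flow oxygen for the remainder of follow-up", so a last score of 7 adds nothing.
- **Deaths (8.2.5).** The plots are drawn "where subject whose days are imputed to the maximum of 28 days due to death are grouped separately from subjects who do not die".

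The two sister outcomes match count to population. "Oxygen days will be defined as the number of days where the clinical status score is equal to 5, 6, or 7" (3.3.8), summarized in baseline 5, 6 or 7 (8.2.3). "Ventilator / ECMO days will be defined as the number of days where the clinical status score is equal to 7" (3.3.7), and for the summary: "This will only include subjects in category 7 at enrollment" (8.2.7).

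SAP 6.4 repeats the secondary outcomes by baseline category, so a baseline-7 row is planned. SAP 8.2.6 identifies new NIV/high-flow use by a score of 6 or more.

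**The concern.** Score 7 is the worse state, and SAP 4.3 records the worst status of each day, so a day with any invasive ventilation scores 7 and is not counted. A subject who enters at 7 can accrue NIV/high-flow days only by improving, and one who enters at 6 loses them by worsening to 7. With deaths placed at the maximum, the scale reads as more days being worse, yet among survivors the sickest course gives the lowest value. An arm in which more ventilated subjects step down to high-flow oxygen can then show more days of support.

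The same split appears in new use. A subject who goes from 5 straight to 7 counts as a new NIV/high-flow user under 8.2.6 but accrues no NIV/high-flow days while at 7.

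**Working it through.** The documents give no numerical figure for this outcome, so there is none to reproduce. The check applies the stated rule to score sequences.

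**Rule.** For a survivor followed in hospital, D = number of days (of 28) with score 6. The comparator is D* = number of days with score 6 or 7. Death gives 28 under both.

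| Survivor's course | D (as written) | D* |
|---|---|---|
| 28 days at 7 | 0 | 28 |
| 10 days at 7, then 8 at 6 | 8 | 18 |
| 10 days at 7, then 5 or better | 0 | 10 |
| 2 days at 6, then 26 at 7 | 2 | 28 |

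The post-discharge CRF question cannot change the first row if the subject is never discharged.

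**Baseline-7 row.** All shares are assumptions. Take 100 per arm with 20 deaths in each; ventilated throughout 50 control, 30 treated; the rest 10 days at 7, then 8 at 6. The median is the mean of the 50th and 51st ordered values.

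- As written, control: 50 at 0, 30 at 8, 20 at 28; median (0 + 8)/2 = 4.
- As written, treated: 30 at 0, 50 at 8, 20 at 28; median 8.
- Counting 6 or 7, control: 30 at 18, 70 at 28; median 28.
- Counting 6 or 7, treated: 50 at 18, 50 at 28; median (18 + 28)/2 = 23.

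If half of the extubated go from 7 directly to 5 or better, the values at 0 as written number 50 + 15 = 65 and 30 + 25 = 55, so the medians tie at 0. Counting 6 or 7 they remain 28 vs 23.

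**Range, 18 settings.** Deaths 10, 20, 30%; ventilated throughout 60 vs 40, 50 vs 30, 40 vs 20%; none or half of the extubated skipping score 6. Control vs treated medians:

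- As written: 0 vs 0 in 6, 8 vs 8 in 3, 0 vs 8 in 4, 4 vs 8 in 3, 0 vs 4 in 2. The treated arm is higher in 9, tied in 9, never lower.
- Counting 6 or 7: 28 vs 23 in 6, 28 vs 28 in 6, 28 vs 18 in 4, 23 vs 18 in 2. The treated arm is lower in 12, tied in 6, never higher.

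**Pooled 8.2.5 table, 15 settings.** Baseline-6 share 30, 40, 50, 60, 70%. Baseline 6 is the same in both arms: 10% deaths, 15% with 2 days at 6 then 26 at 7, 75% with 6 days at 6. Baseline 7 has 20% deaths and the three ventilated-throughout contrasts above. As written:

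- All extubated pass through 6: median 6 vs 6 in 12 and 6 vs 8 in 3; Q1 higher for treated in 13, tied in 2.
- Half skip 6: median tied in 13; Q1 higher for treated in 3, tied in 12; Q3 higher for treated in 7.

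**Restricting to baseline 6 and score 6.** Assume 10% deaths; worsening subjects have 2 days at 6 then 26 at 7; the rest have 6 days at 6.

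- Worsening 50 vs 30%: control has 50% at 2 and 40% at 6, median (2 + 6)/2 = 4; treated has 30% at 2, median 6.
- 60 vs 40%: median 2 vs 6.
- 30 vs 10% and 40 vs 20%: medians tie at 6, but Q1 is 2 vs 6, because more than 25% of controls sit at 2.

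**The case against.** The strongest defence is that this is a count of one modality. Protocol Section 3 lists NIV/high-flow and invasive ventilation as separate outcomes, a subject ventilated throughout has had no NIV days, and the SAP nowhere says that fewer days are better. That stands for the count rule taken alone. It does not explain why 8.2.5 admits baseline-7 subjects, or why deaths take the maximum, which does not fit a plain modality count. The sister outcomes show the pattern that this one breaks.

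The defence is right on size. No test is planned for this outcome, ventilated time is still captured in oxygen days (and in ventilator days for baseline 7), and half of the 18 baseline-7 settings tie. Table 43 has no shell of its own, only a note that it resembles Table 41, so nothing here rests on its row labels.

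A reader might infer three stronger things that the documents do not support:

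- That the problem sits only in the baseline-7 row. It does not: a move from 6 to 7 also cuts the count for baseline-6 subjects.
- That the pooled table is distorted mainly in its lower quartile. That depends on how many extubated subjects pass through score 6, which the documents do not give.
- That trial conclusions on recovery or Day 15 status are touched. Those endpoints are defined separately and do not use this count.

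**Conclusion.** The mismatch holds as a matter of text: the count rule in 3.3.6, the imputation in 6.5 and the population in 8.2.5 do not describe the same quantity, and among survivors the ordering can reverse. In the baseline-7 row the assumed case gives 4 vs 8 where counting 6 or 7 gives 28 vs 23. Across the assumed range the treated arm is higher or tied as written. In the pooled table the effect is small, and the quartile affected is not determined. Every share used is an assumption, so these figures show direction and possible size; they are not predictions. Severity is minor: one descriptive, untested, non-key secondary outcome and its subgroup rows.

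**What to change.** Use one definition in 3.3.6, 6.5, 8.2.5, the Table 43 labels and the new-use duration in 8.2.6. There are two consistent choices.

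- **Score 6 or 7 in baseline 6 or 7**, labelled as NIV/high-flow or higher support, with new-use duration also on 6 or 7 and the score-6 count kept as supplementary. This removes the reversal. Its cost is overlap with ventilator days and some departure from the protocol's separate outcomes.
- **Score 6 in baseline 6 only**, with new-use duration also on score 6. This removes the baseline-7 zeros and keeps the outcomes separate. Its cost is the residual reversal shown above when subjects worsen from 6 to 7. State that limit, and read the result beside ventilator days and new use by score 7.

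Also:

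- State which post-discharge CRF days feed which outcome, since 3.3.6 and 3.3.7 cite the same question.
- Correct 8.2.8, which is headed and worded as NIV/high-flow but identifies use by score 7.
- Reconcile the sentences limiting 8.2.6 and 8.2.8 to category 4 with the wider populations (4 or 5; 4, 5 or 6) given in the same paragraphs.
- State whether death (score 8) counts as new use in 8.2.4 and 8.2.6. Their thresholds of 5 or more and 6 or more include it; the score of 7 in 8.2.8 does not.

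The work is SAP wording, table labels and derivation code, with no new data. SAP 2.1 records that interim efficacy results were already public, so document the change as made after that disclosure.
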